9. SAMPLE SIZE AND PROPOSED RECRUITMENT RATE

[figure not shown]
9.1 Sample size and recruitment rate

A sample size of 60 women will be sufficient to identify any potential problems in feasibility which have a 5% probability of occurrence, with 95% confidence. A pilot study of this size will also give a precise estimate of the standard deviation for a small effect size in a future phase 3 effectiveness trial with 90% power and two-sided 5% significance.^{21,22}

We aim to recruit a total of 74 women to allow for 20% attrition based on our previous RCTs in this field (SIMS¹⁷ and OPAL²³). In our detailed survey of practice in 64 potential collaborating centres, recruitment estimates ranged from 8 to 50 participants per month. We used a conservative estimate

of 4-6 centres, each recruiting 3-4 per month per centre, to achieve our target of 74 participants over a 6-month recruitment period.

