4. TRIAL RECRUITMENT

4.1 Trial population

Women aged 18 years or over with stress predominant UI who have been referred to the collaborating gynaecology, urology or urogynaecology within hospitals across the UK. We aim to recruit and randomise 74 women (37 in each arm).

For the purposes of this trial, the term 'women' includes all people with a vagina and assigned female sex at birth.

Setting: secondary and tertiary care acute hospital settings across the UK. NHS Grampian will be the clinical co-ordinating centre and house the Chief Investigator (CI)

Women will be approached and recruited by HCPs in UK hospitals in Scotland and England representing diverse geographical and socio-economic characteristics. The hospitals will be chosen to represent the practice in the UK and will include a mix of urban and rural, tertiary and secondary care and serve ethnically and socio-economic diverse populations. Each unit will have at least one participating healthcare professional who is comfortable prescribing VCDs.

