We will use various methods to collect the outcomes (paper/electronic) according to participants' choice, to maximise response rates. Non-responders will receive two reminders; the first is by their preferred method of contact (postal, text message, email) and the second reminder will be a postal one-page short questionnaire. For non-responders after this second reminder, we will use an automated text/interactive voice recognition application to collect information on how their incontinence has been in the last two weeks compared to when they joined the study (the single question in section 5 of the follow-up questionnaire). We have selected this question to focus this data collection on as this is the most likely primary outcome for a larger future trial. This data collection will apply to participants who have supplied us with their mobile phone number and consent to contact them via phone. Initially the system sends the participant a text identifying the study and asking the participant to complete the primary outcome question via the link provided. If the participant chooses not to use the link to respond, the IVR will attempt to call the participant. The IVR message will be played if the call is answered, and women will be asked to confirm that they are the participant. If they confirm they are the participant, the IVR will read the question and women will be able record their response. If the call is not answered, no message will be left. This data collection system has been successfully implemented in a previous study (SIMS).

The qualitative study embedded within the pilot RCT is described in section 8.

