9.2 Gantt chart

10. STATISTICAL ANALYSIS

The statistical analysis is outlined fully in a separate statistical analysis plan. All main analyses will be based on the Intention-to-Treat (ITT) principle. Analysis will take place after full recruitment and follow-up is complete. The focus will be on tabulated and associated graphical summaries of the key indicators of success of the pilot.

We will report data in line with the Consolidated Standards of Reporting Trials (CONSORT) 2010 extension statement for Pilot and Feasibility trials showing attrition rates and loss to follow-up.

As the primary outcome is the feasibility of achieving 80% of the target within 6 months it is a simple summary of the number of participants recruited and there is no uncertainty on this count. The number identified as eligible is also an exact number as are the numbers who drop out from receiving the intervention, withdraw consent and fail to provide follow-up data. These numbers can be used to calculate the percentage of eligible participants who enter the trial, adhere to their allocated intervention and also estimate the loss to follow-up percentage. Confidence intervals will be obtained for these percentages too.

The success rate from the PGI-I, adverse events will be summarised with count and percentage while the specific UI outcomes and waiting time for physiotherapy will be summarised with mean and standard deviation. The UI outcomes and PGI-I success rate will be compared using the appropriate linear regression model with adjustment for the baseline outcome where possible to obtain a treatment effect and 95% confidence interval. Adverse event rates will be compared between the groups using the appropriate linear model to obtain a relative risk.

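### The 95% assurance of seeing a 5% feasibility problem holds for problems any participant can have, but is 79–85% for problems that only women allocated a VCD can have

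*Protocol*

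**What the plan says.** Protocol section 9.1 gives two reasons for the sample size. The first is that 60 women are "sufficient to identify any potential problems in feasibility which have a 5% probability of occurrence, with 95% confidence". The second is that a pilot of this size will "give a precise estimate of the standard deviation for a small effect size" in a later trial with 90% power and two-sided 5% significance. The target is then raised for dropout: "We aim to recruit a total of 74 women to allow for 20% attrition". Section 4.1 gives the split between arms: "We aim to recruit and randomise 74 women (37 in each arm".

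Three other places bear on the point:
- Section 3.2 says it is unclear whether the devices are easy to insert. Sections 3.2 and 4.11 make special arrangements for centres where a device may be hard to obtain. Section 7.2 lists events that only a device user can have.
- Section 4.9 says of the single question on change in incontinence that "this is the most likely primary outcome for a larger future trial".
- Section 10 states that "The success rate from the PGI-I, adverse events will be summarised with count and percentage", and keeps mean and standard deviation for the UI outcomes and physiotherapy waiting time.

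**The concern.** The rule behind the first reason counts women who could each show the problem. Section 9.1 applies it to all 60 women and to every kind of feasibility problem, without saying that the denominator changes for device problems. Both arms receive supervised PFMT, so the device is what separates them, and only half the women are allocated one. If no case of some device problem is seen in 30 to 37 users, a reader of section 9.1 would take more comfort from that than the design gives.

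A smaller matter concerns the second reason. It does not name the outcome whose standard deviation is meant. The question in section 4.9 matches the description of the PGI-I, and section 10 treats the PGI-I as a success rate. For a success rate the planning input is a proportion, and section 9.1 gives no precision for it.

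**Working it through.** **Inputs.** Problem frequency 5%, confidence 95%, 60 women, 74 recruited, 20% attrition (section 9.1); 37 per arm (section 4.1).

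**The protocol's own figure.** The chance of seeing at least one case among n women is 1 − (1 − p)^n. For 95% at p = 0.05:
- n = ln(0.05)/ln(0.95) = 58.4, so 59 women.
- n = 59: 1 − 0.95^59 = 95.2%.
- n = 60: 1 − 0.95^60 = 95.4%.
- After attrition: 74 × 0.8 = 59.2, so 59 women remain and the assurance holds.

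The stated figure reproduces for problems any participant can have, such as questionnaire return or missed PFMT appointments.

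**Problems only VCD users can have.** All 37 women count if the problem shows before dropout. After 20% attrition, 37 × 0.8 = 29.6, about 30.

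| VCD women observed | Chance of seeing a 5% problem at least once | Smallest frequency seen with 95% confidence, 1 − 0.05^(1/n) |
|---|---|---|
| 37 | 1 − 0.95^37 = 85.0% | 7.8% |
| 30 | 1 − 0.95^30 = 78.5% | 9.5% |

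**Same result per randomised woman.** With 1:1 allocation, 5% of VCD users is about 2.5% of all women randomised. Then 1 − 0.975^60 = 78.1% and 1 − 0.975^74 = 84.6%. Changing the denominator does not restore 95%.

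**Standard deviation sentence.** With 60 women in two arms (58 degrees of freedom), the 95% interval for a standard deviation runs from 0.85 to 1.22 times the estimate. If small is taken as a standardised effect of 0.2 (an assumption; section 9.1 gives no number), the combined size of pilot and main trial is 1,160 with either 25 or 30 per arm in the pilot, close to the optimum of about 24. So 60 is reasonable for a continuous outcome.

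**PGI-I success rate.** The 95% half-width per arm is 1.96 × √(p(1 − p)/n). With n = 30 it is 16.4 points at p = 0.3 or 0.7 and 17.9 points at p = 0.5. The range of p is an assumption; the protocol gives no expected rate.

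**The case against.** The strongest reply is that nothing has been miscalculated: 60 women do give 95% for a 5% problem among participants, and 79–85% answers a different question. That stands, and it is why the point concerns scope. It does not remove the point, because the sentence covers every feasibility problem and the trial is partly about device problems.

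Four further replies also carry weight:
- **The 79% is a worst case.** Sites organise the device for each woman allocated to it (section 4.11), use and side effects are also asked at 3 months (section 4.9), and adverse events go on case report forms as well as questionnaires (section 7.4). Supply and early insertion problems can appear before dropout, so 85% is nearer the mark for those.
- **Adherence is not a fair example.** It is a proportion judged against cut-offs in Table 1, not an event to be seen once.
- **No decision uses the figure.** The progression criteria in Table 1 rest on recruitment, retention and adherence.
- **Other sources exist.** The interviews and focus groups in section 8 also look at device attitudes, fidelity and adherence.

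Three stronger readings are tempting but unsupported:
- **That the target is wrong**, because 60/0.8 = 75 and not 74. This is rounding: 74 still leaves the 59 women needed.
- **That the standard deviation argument contradicts section 4.9.** Section 9.1 does not tie it to the PGI-I, it fits the continuous UI scores, the future primary outcome is only described as likely, and establishing relevant outcomes is objective 2.
- **That the imprecise success rate leaves the definitive trial's size wide open.** Take an assumed control rate of 50%, with 95% Wilson interval 33–67% at n = 30, and n per arm = 10.507 × (p1q1 + p2q2)/(p2 − p1)². A fixed success ratio of 1.2 gives about 220 to 1,110 per arm, but a fixed 10-point difference gives only about 420 to 520. The wide range comes from choosing a ratio that the protocol does not state.

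**Conclusion.** The 95%/5% statement in section 9.1 is correct for problems common to both arms and too broad for problems confined to the VCD arm. There the assurance is 85% with all 37 women and 79% with 30, or 95% only for problems of at least 7.8% to 9.5%. These figures assume 1:1 allocation with 37 per arm, independent women, and, for the lower figure, 20% attrition before the problem could be observed.

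A reader might infer that the trial is too small. The documents do not support that. Keeping 95% at 5% within the VCD arm would take 59 observed users, hence 74 in that arm (59/0.8 = 73.75) and 148 in total, but no objective or progression criterion requires it.

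The standard deviation sentence is a minor matter of naming the outcome. No analysis or progression rule changes.

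**What to change.** In section 9.1:
- Limit the 95%/5% statement to problems that can affect women in either arm.
- Add that, for problems specific to VCD users, the chance of seeing a 5% problem at least once is 85% (n = 37) to 79% (n = 30), or equivalently that 95% confidence applies to problems of at least 7.8% to 9.5%.
- As a minor wording change, say that the standard deviation sentence refers to the continuous ICIQ scores. Note that the PGI-I success rate will be estimated to about ±16–18 points per arm (n = 30, assuming a true rate of 30–70%).

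The change is text only and needs no more women. Its one cost is a slightly less favourable stated figure.

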9.2 Gantt chart

10. STATISTICAL ANALYSIS

The statistical analysis is outlined fully in a separate statistical analysis plan. All main analyses will be based on the Intention-to-Treat (ITT) principle. Analysis will take place after full recruitment and follow-up is complete. The focus will be on tabulated and associated graphical summaries of the key indicators of success of the pilot.

We will report data in line with the Consolidated Standards of Reporting Trials (CONSORT) 2010 extension statement for Pilot and Feasibility trials showing attrition rates and loss to follow-up.

As the primary outcome is the feasibility of achieving 80% of the target within 6 months it is a simple summary of the number of participants recruited and there is no uncertainty on this count. The number identified as eligible is also an exact number as are the numbers who drop out from receiving the intervention, withdraw consent and fail to provide follow-up data. These numbers can be used to calculate the percentage of eligible participants who enter the trial, adhere to their allocated intervention and also estimate the loss to follow-up percentage. Confidence intervals will be obtained for these percentages too.

The success rate from the PGI-I, adverse events will be summarised with count and percentage while the specific UI outcomes and waiting time for physiotherapy will be summarised with mean and standard deviation. The UI outcomes and PGI-I success rate will be compared using the appropriate linear regression model with adjustment for the baseline outcome where possible to obtain a treatment effect and 95% confidence interval. Adverse event rates will be compared between the groups using the appropriate linear model to obtain a relative risk.

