	and nurses) regarding VCDs as a management option for SUI, key outcomes of importance from both women and for HCPs perspectives, and ethical/practical issues impacting on trial participation and provision of trial. Qualitative study will involve one-to-one semi-structured interviews with 9-15 women and focus groups with 8-10 HCPs from across the participating sites. All interviews and Focus group data will be coded inductively and deductively, and the analysis organised using - Framework' analysis approach.
Statistical methods	
The number of eligible participants, number of individuals who consent, and number recruited will be presented both in tables and graphs using count and percentage.
 
The number and percentage of recruited participants who decline their allocated intervention, withdraw consent and fail to provide outcome data will also be presented in tabular form.
 
For the various outcome measures, the appropriate linear model will be used to obtain a treatment effect and 95% confidence interval. A repeated measures analysis corrected for baseline will be used where appropriate.

Co-ordination	
Local: by local research teams
 
Central: by Trial Office in Aberdeen ([contact], [name]).
 
Overall: by the Project Management Group and overseen by the Trial Steering Committee and the Data Monitoring Committee.

LAY SUMMARY

Urinary incontinence (UI) is common and debilitating, affecting >6million UK women over age of 40years, causing embarrassment, low self-esteem, social isolation, and reduced productivity. First-line treatment is pelvic floor muscle training (PFMT), but currently one in three women still proceed to surgery.

Vaginal continence devices (VCDs), worn inside the vagina, support the bladder to help achieve continence. Guidelines recommend VCDs are used when PFMT is not effective on its own. Combining VCDs with PFMT might be more effective for treating UI than PFMT alone, improving quality of life (QoL) and reducing the need for surgery. VCDs are widely used, despite little evidence about their benefits, risks and whether they provide value-for-money.

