4.9 Follow-up procedures

At baseline, participants will be asked for their contact preferences for questionnaires. If they select email or text messaging, the email and/or mobile number will be verified automatically via the study website. Once an email address is verified, those selecting email as their preference will have a link to the questionnaire emailed to them. Those selecting post as their preference will have the questionnaire posted to them. Once an email number is verified, those selecting text messaging as their preference will have a link to the questionnaire texted to them.

The trial office will be responsible for entering all questionnaire data returned by post into the study website.

Questionnaires will be administered to all participants who were randomised in the study, regardless of their compliance to the randomised treatment unless they have opted out of questionnaire follow-up.

If questionnaires are returned as non-deliverable, attempts will be made by site staff or staff at the Trial Office to trace the participant via the local sites and/or the GP.

Consenting Participants will be asked, at baseline, to complete the baseline questionnaire which includes questions on participants' demographic details, their general health and relevant medications. It also comprises validated questionnaires for symptom severity of UI and its impact on quality of life (QoL) and sexual function: International Consultation on Incontinence Questionnaire - Lower Urinary Tract Symptoms Questionnaire (ICIQ-FLUTS), disease specific QoL questionnaire (ICIQ-LUTSql) and the International Consultation on Incontinence Questionnaire Female Sexual Matters Associated with Lower Urinary Tract Symptoms (ICIQ-FLUTSsex).

The above questionnaires will also be completed at 3- and 6-months post-randomisation. In addition, participants will be asked to complete the Patient Global Impression of Improvement (PGI-I), a validated single-item tool assessing women's perception of improvement. They will also be asked to report any side effects, further treatment received for UI, adherence to PFMT and use of VCDs, as well as reasons for non-adherence. The questionnaires will also collect information on frequency and duration of VCDs use, and types of VCDs used by participants.

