6. DATA COLLECTION AND PROCESSING

6.1 Measuring outcomes

A baseline questionnaire will be completed prior to randomisation. Follow-up questionnaires will be sent at 3 and 6 months post-randomisation. Table 2 summarises the sources and timing of outcomes measures.

Table 2: Outcome measures

	Baseline	3-months	6-months
Clinical assessment	○		
ICIQ-FLUTS (International Consultation on Incontinence Questionnaire - Lower Urinary Tract Symptoms Questionnaire)	○	●	●
ICIQ-LUTSqol International Consultation on Incontinence Questionnaire - Lower Urinary Tract Symptoms Quality of Life Questionnaire	○	●	●
ICIQ-FLUTSsex International Consultation on Incontinence Questionnaire Female Sexual Matters Associated with Lower Urinary Tract Symptoms	○	●	●
PGI-I		●	●
Adverse events		●	●

○ At clinic appointment or by post/ email

● By post, email, text – according to participant's preference

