6.2 Baseline

The baseline questionnaires will collect information about participants' age, parity, smoking status, previous treatment, severity of urinary incontinence and ethnicity. As described, the following questionnaires are also included in the Baseline-pack: ICIQ-FLUTS, ICIQ-LUTSqol, ICIQ-FLUTSsex.

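### The baseline-adjustment rule in section 10 names no covariate for PGI-I success, which has no baseline; naming baseline ICIQ-FLUTS would be a small, nearly free gain in precision

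*Protocol*

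**What the plan says.** Protocol section 10 covers the two kinds of clinical outcome in one sentence: "The UI outcomes and PGI-I success rate will be compared using the appropriate linear regression model with adjustment for the baseline outcome where possible". The result is to be a treatment effect with a 95% confidence interval. The statistical methods row of the Trial Summary is similar in spirit: "A repeated measures analysis corrected for baseline will be used where appropriate". Section 10 also opens by deferring detail: "The statistical analysis is outlined fully in a separate statistical analysis plan".

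Section 4.9 introduces the PGI-I at follow-up, after listing the questionnaires that are completed at baseline and repeated later: "In addition, participants will be asked to complete the Patient Global Impression of Improvement (PGI-I), a validated single-item tool assessing women's perception of improvement". Table 2 agrees, with entries for the PGI-I at 3 and 6 months and none at baseline.

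Measures of severity at entry are collected. Section 6.2 lists "previous treatment, severity of urinary incontinence and ethnicity" among the baseline items and puts ICIQ-FLUTS in the baseline pack. Section 6.1 fixes the timing: "A baseline questionnaire will be completed prior to randomisation". Randomisation (section 4.8) is stratified by centre and by type of incontinence, and neither measures severity.

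Section 4.9 reserves the last-resort text or voice contact for a single item on how the woman's incontinence compares with its state at trial entry, on the ground that "this is the most likely primary outcome for a larger future trial".

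**The concern.** The rule works for the ICIQ scores, each of which has its own pre-randomisation value. It cannot work for the PGI-I, which rates change since entry and so has no entry value. The words that allow for this case let the adjustment lapse; they do not name a substitute, although a natural one is collected for every woman before allocation.

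Severity at entry may well affect how much improvement a woman can report. If it does, leaving it out of the model gives up precision, and the estimate from a very small trial carries whatever chance imbalance in severity arises. The single item in section 4.9 is probably the PGI-I, because that is the only follow-up instrument the protocol describes as a single-item rating of improvement. The outcome most likely to carry the definitive trial would then have the least developed stated analysis.

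**Working it through.** **The plan's own figures.** The protocol gives no figure on covariate adjustment, so the starting point is the sample size in section 9.1.

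- Detecting a problem of 5% probability with 95% confidence: n = ln(0.05)/ln(0.95) = 58.4, so 59. The protocol states 60, which gives 1 − 0.95^60 = 95.4%.
- Allowing for 20% attrition: 59/0.8 = 73.75, so 74 as stated (60/0.8 = 75).
- Women with outcome data: 74 × 0.8 = 59.2, about 30 per arm under 1:1 allocation.

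These figures reproduce and do not depend on the adjustment.

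**Assumed inputs.** The protocol gives neither a PGI-I success rate nor a correlation r between baseline severity and PGI-I success. I take 50% success in both arms and r from 0.2 to 0.4.

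**Unadjusted interval.** Half-width = 1.96 × sqrt(0.5 × 0.5/30 + 0.5 × 0.5/30) = 0.253, or 25.3 percentage points.

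**Adjusted interval.** On the linear scale, a covariate with correlation r multiplies the standard error by about sqrt(1 − r²). A simulation of 6,000 trials with 30 women per arm and a linear probability model gives slightly smaller gains at r = 0.3 and 0.4 and a slightly larger standard error throughout:

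| r | Factor, formula | Half-width, formula | Factor, simulation | Half-width, simulation |
|---|---|---|---|---|
| 0.2 | 0.980 | 24.8 | 0.985 | 24.9 |
| 0.3 | 0.954 | 24.1 | 0.965 | 24.4 |
| 0.4 | 0.917 | 23.2 | 0.925 | 23.4 |

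The half-width falls by 0.5, 1.2 and 2.1 points by formula, and by 0.4, 0.9 and 1.9 points in simulation: roughly 0.5 to 2 points.

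**Chance imbalance.** The difference in baseline means between arms, in units of the baseline SD, has standard deviation sqrt(2/30) = 0.258. Its 95% limit is 1.96 × 0.258 = 0.506. The resulting shift in the unadjusted difference in success is imbalance × r × 0.5, where 0.5 is the SD of a binary outcome at 50%:

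| r | Shift at a one-SD imbalance (0.258) | Shift at the 95% limit (0.506) |
|---|---|---|
| 0.2 | 2.6 points | 5.1 points |
| 0.3 | 3.9 points | 7.6 points |
| 0.4 | 5.2 points | 10.1 points |

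The unadjusted interval of about ±25 points already allows for this variation.

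**The case against.** The strongest reply is that covariates for a secondary outcome belong in the SAP, which section 10 says contains the full analysis and which was not available here. A reader might infer that the PGI-I will be analysed with no severity adjustment at all, or that only an outcome's own baseline may enter a model. The text supports neither: it names one adjustment, excludes no other, and its qualifier already allows for an outcome with no baseline. There is no contradiction in the protocol. That much of the objection stands. What remains is narrower than a missing covariate list: the protocol states a rule, applies it by name to PGI-I success, and the rule cannot operate there.

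A reader might also infer that the unadjusted result is biased. It is not: under randomisation the comparison is valid, and its interval covers chance imbalance. Shifts of 5 to 10 points are not what should be expected either; they arise at the 95% limit of imbalance under an assumed correlation.

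It is also fair to say that section 4.9 does not name the PGI-I as the likely future primary outcome. The link is a reasonable inference. Finally, the pilot's primary outcome is recruitment, and Table 1 rests progression on recruitment, retention and adherence, so no decision in this trial turns on the PGI-I effect. Nor would adjustment put a binary success rate and continuous ICIQ scores on a comparable footing; they are on different scales in any case.

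**Conclusion.** The point holds as an optional improvement, not as an error. The stated rule gives PGI-I success no covariate, while a suitable one is collected before randomisation. The comparison remains valid, and no feasibility or progression conclusion is affected. The cost of leaving the text as it is amounts to roughly 0.5 to 2 percentage points on a half-width of about 25.

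That size rests on about 30 women per arm, 50% success, and a correlation of 0.2 to 0.4 that the documents do not supply; a weaker correlation would make the gain negligible. It is worked out for a difference in proportions on the linear scale, and the protocol leaves the exact model open.

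**What to change.** In section 10, and carried into the SAP before outcome data are seen, state that the UI outcomes are adjusted for their own baseline value and that PGI-I success is adjusted for the baseline ICIQ-FLUTS score. Also report the observed association between baseline severity and PGI-I success. Objective 3 asks for a reliable sample size for the definitive trial, and that association would inform it.

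The cost is a short rewording and one extra term in the PGI-I model. No new data are needed, and the sample size does not change.

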4.8 Randomisation and allocation

Eligible participants, who have signed the informed consent form, will be randomised to one of the two study groups in a 1:1 allocation ratio. A randomisation application hosted by CHaRT will be used for this purpose. This is available 24 hours a day by means of a web-based randomisation application. Random allocation will use a stratification algorithm based on:

- collaborating centre
- type of urinary incontinence (pure Stress Urinary Incontinence or stress-predominant mixed urinary incontinence)

The type of urinary incontinence will be as per the HCP assessment at the time of review at the clinic.

Consenting patients will be randomised to VCDs plus PFMT or to PFMT-only as close as possible to receiving the interventions. Participants in the VCD plus PFMT arm will be prescribed and/or start using their VCDs at the time (or as close as practically possible) to their first physiotherapy appointment.

A person with delegated authority will access the web-based system. The trial is not blinded - at randomisation, an email will be sent to the collaborating site research team, including the PI, and the trial office, informing them of the allocation.

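### Allocation is stratified by centre and type of incontinence, but the only covariate the protocol names for the between-group models is the baseline outcome

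*Protocol*

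**What the plan says.** Section 4.8 states that participants "will be randomised to one of the two study groups in a 1:1 allocation ratio" and that "Random allocation will use a stratification algorithm based on" two factors: the "collaborating centre", and whether incontinence is pure stress or stress-predominant mixed. Section 9.1 plans for 4-6 centres.

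Section 10 compares the incontinence outcomes and the PGI-I success rate with a suitable linear regression model, "with adjustment for the baseline outcome where possible to obtain a treatment effect and 95% confidence interval". The statistical methods entry of the trial summary adds: "A repeated measures analysis corrected for baseline will be used where appropriate". For safety, section 10 says: "Adverse event rates will be compared between the groups using the appropriate linear model to obtain a relative risk", with no covariate named. Centre and type of incontinence are not named as model terms anywhere in the protocol.

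On timing, section 6.1 says that "Table 2 summarises the sources and timing of outcomes measures". In that table the three ICIQ questionnaires are marked at baseline, 3 and 6 months, and PGI-I at 3 and 6 months only.

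Section 10 also refers the full analysis to a separate statistical analysis plan, which is not available here.

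**The concern.** Stratified allocation balances the arms on centre and type of incontinence. If those factors predict outcome, the balance makes the treatment estimate more precise. A model that omits them leaves their variation in the residual, so the reported standard error is larger than the true sampling error and the interval covers more than 95%. Including the factors recovers that precision.

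The protocol is not silent on adjustment. It names a covariate in two places, and in neither place are the stratification factors mentioned. Someone following the wording would fit treatment plus baseline for the ICIQ scores and treatment alone for PGI-I.

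The stake is modest. The treatment-effect intervals are secondary here. However, section 9.1 justifies the pilot's size partly by the standard deviation it will supply for a later trial. If that trial is planned on a residual standard deviation from a model without the strata, the figure will be too large wherever the strata matter. There is some reason to think centre could matter, since sections 3.1 to 3.3 let device choice and the training programme follow each hospital's standard practice. The documents give no effect size for either factor.

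**Working it through.** **The plan's own figures.** Section 9.1 gives 60 women to detect a feasibility problem of 5% probability with 95% confidence: ln(0.05)/ln(0.95) = 58.4, so 59, and 60 women give 1 - 0.95^60 = 95.4%. For 20% attrition, 59/0.8 = 73.75, so 74 (60/0.8 = 75). These figures reproduce and are not in question. They give the number analysed: 74 × 0.8 = 59.2, about 59. The protocol states no interval width or standard deviation for any treatment effect, so there is no planned precision to reproduce.

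**Inputs.** From the documents: 74 randomised 1:1, 20% attrition, 4-6 centres, two types of incontinence. Assumed: a 50:50 split by type, permuted blocks of 4 within centre by type, one continuous outcome at one follow-up time, and R², the share of the variance left after baseline that the strata explain.

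**Formula.** The ratio of the 95% interval half-widths, with strata to without, is √(1 - R²) × t(df₂)/t(df₁), where t is the 97.5% point. With 59 women, df₁ = 59 - 3 = 56. Adding type (1 term) and centre (3 or 5 terms) gives df₂ = 52 or 50. The formula ignores chance imbalance between arms within strata, so it was checked by simulation with 4,000 trials per setting, comparing treatment + baseline with treatment + baseline + type + centre.

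| R² | Width ratio by formula, 4 / 6 centres | Width ratio by simulation, 4 / 6 centres | Coverage of baseline-only interval, 4 / 6 centres |
|---|---|---|---|
| 0 | 1.002 / 1.003 | 1.013 / 1.021 | 94.78% / 94.88% |
| 0.05 | 0.976 / 0.977 | 0.986 / 0.995 | 95.45% / 95.40% |
| 0.10 | 0.950 / 0.951 | 0.961 / 0.970 | 96.25% / 95.40% |
| 0.20 | 0.896 / 0.897 | 0.902 / 0.911 | 96.62% / 96.70% |
| 0.30 | 0.838 / 0.839 | 0.842 / 0.849 | 97.58% / 97.08% |

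Coverage of the adjusted interval stayed between 94.8% and 95.4%. The Monte Carlo standard error near 95% is √(0.95 × 0.05/4000) = 0.34 percentage points, so the coverage at R² = 0.05 is not clearly different from nominal.

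**Reading the table.** In the simulation, adjusting narrows the interval by 0.5-1.4% at R² = 0.05, 3-4% at 0.10, 9-10% at 0.20 and 15-16% at 0.30. It widens it by 1-2% at R² = 0. Scaling the R² = 0 ratio by √(1 - R²), the two models break even at R² = 1 - 1/1.0132² = 0.026 with 4 centres and 1 - 1/1.0214² = 0.041 with 6.

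**Residual standard deviation.** Omitting the strata inflates it by about 1/√(1 - R²): 1.026, 1.054, 1.118 and 1.195 at R² = 0.05, 0.10, 0.20 and 0.30.

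**Not computed.** PGI-I success is binary, and no gain was derived for it or for adverse events.

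**The case against.** The strongest objection is that covariate lists belong in the statistical analysis plan, to which section 10 defers. A reader might infer from section 10 that the models adjust for baseline and nothing else. The text does not say that. It speaks of an appropriate model and adjustment where possible, and never excludes the stratification factors. The unseen plan may include them. This stands, and limits the point to what the protocol names. It does not remove the point, because a protocol that specifies one covariate twice and omits the design factors invites the narrower model.

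A reader might also infer that the intervals are certainly too wide, or wrong. Neither follows. A baseline-only interval is not biased and does not under-cover. It is wider only if the strata predict outcome beyond baseline, for which the documents give no figure. If they do not, adjustment is slightly worse.

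Third, PGI-I may look like the worst case, since it would have no covariate. But an improvement rating cannot have a baseline value, so its absence from Table 2 is no defect. On an odds-ratio scale, adding prognostic covariates usually does not narrow the interval. No loss of precision for PGI-I is claimed.

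Finally, putting centre into every model could do harm. With 4-6 centres and two types there are 8-12 cells for about 59 women, roughly 5-7 per cell. A relative-risk model for uncommon adverse events may not converge with centre terms, and a random-effect variance is poorly estimated from 4-6 centres. This stands and narrows the remedy.

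**Conclusion.** The point holds in a limited form. The protocol randomises on two factors and names neither for the between-group models. If fitted as worded, the models for the continuous incontinence outcomes give conservative intervals and an inflated residual standard deviation in proportion to how far the strata predict outcome.

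The plausible gain from adjusting is a 1-4% narrower interval for R² of 0.05-0.10 and 9-16% for 0.20-0.30, against a 1-2% loss at R² = 0. These sizes rest on an assumed R², block size and type split, and on a single-time-point linear model. They do not carry over to PGI-I or adverse events.

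Severity is low. The primary outcome is a recruitment count, the Table 1 progression criteria are recruitment, retention and adherence, and section 10 puts the emphasis on descriptive summaries. None of these depends on a treatment-effect interval.

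**What to change.** In section 10 and the statistical methods entry of the trial summary, state that:

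- models for the continuous incontinence outcomes include type of incontinence and centre as well as the baseline value, with centre as a random effect or small centres pooled under a rule set before the outcome data are seen;
- the PGI-I comparison includes the two stratification factors where the model converges, with a named fallback where it does not;
- adverse-event comparisons are unadjusted, or adjusted only where event counts allow.

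If the statistical analysis plan already specifies this, align the protocol wording with it.

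The cost is a few sentences and 4 to 6 degrees of freedom if centre is fitted as fixed terms (3 to 5 for centre, 1 for type), or about 1-2% in interval width if the strata turn out not to matter. No new data are needed, because both factors are recorded for randomisation.
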